## **10.5 APPENDIX 5: GENETICS**

**10.6 APPENDIX 6: LIVER AND OTHER SAFETY: SUGGESTED ACTIONS AND FOLLOW-UP ASSESSMENTS**

Not applicable.

**10.7 APPENDIX 7: AES, ADES, SAES, SADES, USADES AND DEVICE DEFICIENCIES: DEFINITIONS AND PROCEDURES FOR RECORDING, EVALUATING, FOLLOW-UP, AND REPORTING IN MEDICAL DEVICE STUDIES**

Not applicable.

**10.8 APPENDIX 8: COUNTRY-SPECIFIC REQUIREMENTS**

**10.8.1 Amendment for Germany**

Section 1.3 **Schedule of Activities (SoA)** ([Section 1.3](#)), Section 5.2 **Exclusion Criteria** ([Section 5.2](#)) and Section 10.2 **Clinical Laboratory tests** ([Section 10.2](#))

In Germany, serology for HIV, hepatitis B and C will be tested at screening.

**10.8.2 Amendment for Italy**

Section 1.3 **Schedule of Activities (SoA)** ([Section 1.3](#)), Section 5.2 **Exclusion Criteria** ([Section 5.2](#)) and Section 10.2 **Clinical Laboratory tests** ([Section 10.2](#))

In Italy, serology for HIV, hepatitis B and C will be tested at screening.

## 10.9 APPENDIX 9: RESPONSE EVALUATION CRITERIA IN SOLID TUMORS (RECIST) 1.1

Confirmatory scans should be obtained **at least 4 weeks** following initial documentation of objective response.

Response and progression will be evaluated in this study using the international criteria proposed by the revised Response Evaluation Criteria in Solid Tumors (RECIST) guideline Version 1.1 (1). Changes in the largest diameter (unidimensional measurement) of the tumor lesions and the shortest diameter in the case of malignant lymph nodes are used in the RECIST criteria.

### Selection of Lesions

- **Measurable disease:** Measurable lesions are defined as those that can be accurately measured in at least one dimension (longest diameter to be recorded) as  $\geq 20$  mm ( $\geq 2$  cm) by chest X-ray or as  $\geq 10$  mm ( $\geq 1$  cm) with CT scan, MRI, or calipers by clinical exam. All tumor measurements must be recorded in millimeters (or decimal fractions of centimeters).
- **Malignant lymph nodes:** To be considered pathologically enlarged and measurable, a lymph node must be  $\geq 15$  mm ( $\geq 1.5$  cm) in short axis when assessed by CT scan (CT scan slice thickness recommended to be no greater than 5 mm [0.5 cm]). At baseline and in follow-up, only the short axis will be measured and followed.
- **Non-measurable disease:** All other lesions (or sites of disease), including small lesions (longest diameter  $< 10$  mm [ $< 1$  cm] or pathological lymph nodes with  $\geq 10$  to  $< 15$  mm [ $\geq 1$  to  $< 1.5$  cm] short axis), are considered non-measurable disease. Bone lesions, leptomeningeal disease, ascites, pleural/pericardial effusions, lymphangitis cutis/pulmonitis, inflammatory breast disease, and abdominal masses (not followed by CT or MRI), are considered as non-measurable. Note: Cystic lesions that meet the criteria for radiographically defined simple cysts should not be considered as malignant lesions (neither measurable nor non-measurable) since they are, by definition, simple cysts. ‘Cystic lesions’ thought to represent cystic metastases can be considered as measurable lesions, if they meet the definition of measurability described above. However, if non-cystic lesions are present in the same patient, these are preferred for selection as target lesions.
- **Target lesions:** All measurable lesions up to a maximum of 2 lesions per organ and 5 lesions in total, representative of all involved organs, should be identified as target lesions and recorded and measured at baseline. Target lesions should be selected on the basis of their size (lesions with the longest diameter), be representative of all involved organs, but in addition should be those that lend themselves to reproducible repeated measurements. It may be the case that, on occasion, the largest lesion does not lend itself to reproducible measurement in which circumstance the next largest lesion which can be measured reproducibly should be selected. A sum of the diameters (longest for non-nodal lesions, short axis for nodal lesions) for all target lesions will be calculated and reported as the baseline sum diameters. If lymph nodes are to be included in the sum, then only the short axis is added into the sum. The baseline sum diameters will be used as reference to further characterize any objective tumor regression in the measurable dimension of the disease.

- **Non-target lesions:** All other lesions (or sites of disease) including any measurable lesions over and above the 5 target lesions should be identified as non-target lesions and should also be recorded at baseline. Measurements of these lesions are not required, but the presence, absence, or in rare cases unequivocal progression of each should be noted throughout follow-up.

## Methods for Evaluation of Measurable Disease

All measurements should be taken and recorded in metric notation using a ruler or calipers. All baseline evaluations should be performed as close as possible to the beginning of treatment and never more than 4 weeks before the beginning of the treatment.

The same method of assessment and the same technique should be used to characterize each identified and reported lesion at baseline and during follow-up. Imaging-based evaluation is preferred to evaluation by clinical examination unless the lesion(s) being followed cannot be imaged but are assessable by clinical exam.

- **Clinical lesions.** Clinical lesions will only be considered measurable when they are superficial (eg, skin nodules and palpable lymph nodes) and  $\geq 10$  mm ( $\geq 1$  cm) diameter as assessed using calipers (eg, skin nodules). In the case of skin lesions, documentation by color photography, including a ruler to estimate the size of the lesion, is recommended.
- **Chest X-ray.** Lesions on chest X-ray are acceptable as measurable lesions when they are clearly defined and surrounded by aerated lung. However, CT is preferable.
- **Conventional CT and MRI.** This guideline has defined measurability of lesions on CT scan based on the assumption that CT slice thickness is 5 mm (0.5 cm) or less. If CT scans have slice thickness greater than 5 mm (0.5 cm), the minimum size for a measurable lesion should be twice the slice thickness. MRI is also acceptable in certain situation.
- **PET-CT.** At present, the low dose or attenuation correction CT portion of a combined PET-CT is not always of optimal diagnostic CT quality for use with RECIST measurements. However, if the site can document that the CT performed as part of a PET-CT is of identical diagnostic quality to a diagnostic CT (with IV and oral contrast), then the CT portion of the PET-CT can be used for RECIST measurements and can be used interchangeably with conventional CT in accurately measuring cancer lesions over time. Note, however, that the PET portion of the CT introduces additional data which may bias an investigator if it is not routinely or serially performed.
- **Ultrasound.** Ultrasound is not useful in assessment of lesion size and should not be used as a method of measurement. Ultrasound examinations cannot be reproduced in their entirety for independent review at a later date and, because they are operator dependent, it cannot be guaranteed that the same technique and measurements will be taken from one assessment to the next. If new lesions are identified by ultrasound in the course of the study, confirmation by CT or MRI is advised. If there is concern about radiation exposure at CT, MRI may be used instead of CT in selected instances.

- **Endoscopy, Laparoscopy.** The utilization of these techniques for objective tumor evaluation is not advised. However, such techniques may be useful to confirm complete pathological response when biopsies are obtained or to determine relapse in trials where recurrence following complete response (CR) or surgical resection is an endpoint.
- **Tumor markers.** Tumor markers alone cannot be used to assess response. If markers are initially above the upper normal limit, they must normalize for a patient to be considered in complete clinical response.
- **Cytology, Histology.** These techniques can be used to differentiate between partial responses (PR) and complete responses (CR) in rare cases (eg, residual lesions in tumor types, such as germ cell tumors, where known residual benign tumors can remain). The cytological confirmation of the neoplastic origin of any effusion that appears or worsens during treatment when the measurable tumor has met criteria for response or stable disease is mandatory to differentiate between response or stable disease (an effusion may be a side effect of the treatment) and progressive disease.
- **FDG-PET.** While FDG-PET response assessments need additional study, it is sometimes reasonable to incorporate the use of FDG-PET scanning to complement CT scanning in assessment of progression (particularly possible ‘new’ disease). New lesions on the basis of FDG-PET imaging can be identified according to the following algorithm:
  - a) Negative FDG-PET at baseline, with a positive FDG-PET at follow-up is a sign of PD based on a new lesion.
  - b) No FDG-PET at baseline and a positive FDG-PET at follow-up: If the positive FDG-PET at follow-up corresponds to a new site of disease confirmed by CT, this is PD. If the positive FDG-PET at follow-up is not confirmed as a new site of disease on CT, additional follow-up CT scans are needed to determine if there is truly progression occurring at that site (if so, the date of PD will be the date of the initial abnormal FDG-PET scan). If the positive FDG-PET at follow-up corresponds to a pre-existing site of disease on CT that is not progressing on the basis of the anatomic images, this is not PD.
  - c) FDG-PET may be used to upgrade a response to a CR in a manner similar to a biopsy in cases where a residual radiographic abnormality is thought to represent fibrosis or scarring. The use of FDG-PET in this circumstance should be prospectively described in the protocol and supported by disease-specific medical literature for the indication. However, it must be acknowledged that both approaches may lead to false positive CR due to limitations of FDG-PET and biopsy resolution/sensitivity.

Note: A “positive” FDG-PET scan lesion means one which is FDG avid with an uptake greater than twice that of the surrounding tissue on the attenuation corrected image.

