#### Type of participant and disease characteristics

- I 02. Histologically or cytologically confirmed diagnosis of R/M HNSCC that is considered not amenable to further therapy with curative intent. The eligible primary tumor locations are oropharynx, oral cavity, hypopharynx, and larynx (nasopharynx is excluded).

- I 03. Measurable disease

At least 1 measurable lesion (not biopsied at baseline) per RECIST 1.1 criteria. Target lesion(s) may be located in a previously irradiated field if there is documented radiographic disease progression of such lesion(s).

- I 04. Known HPV p16 status for oropharyngeal cancer.

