## Response Criteria

### Evaluation of Target Lesions

- **Complete Response (CR):** Disappearance of all target lesions. Any pathological lymph nodes (whether target or non-target) must have reduction in short axis to <10 mm (<1 cm).

- **Partial Response (PR):** At least a 30% decrease in the sum of the diameters of target lesions, taking as reference the baseline sum diameters.
- **Progressive Disease (PD):** At least a 20% increase in the sum of the diameters of target lesions, taking as reference the smallest sum on study (this includes the baseline sum if that is the smallest on study). In addition to the relative increase of 20%, the sum must also demonstrate an absolute increase of at least 5 mm (0.5 cm). (Note: the appearance of one or more new lesions is also considered progressions).
- **Stable Disease (SD):** Neither sufficient shrinkage to qualify for PR nor sufficient increase to qualify for PD, taking as reference the smallest sum diameters while on study.

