**10.10.2 Methods of measurement**

The same method of assessment and the same technique should be used to characterize each identified and reported lesion at baseline and during follow-up. Assessments should be identified on a calendar schedule and should not be affected by delays in therapy. While on study, all lesions recorded at baseline should have their actual measurements recorded at each subsequent evaluation, even when very small (eg, 2 mm). If it is the opinion of the radiologist that the lesion has likely disappeared, the measurement should be recorded as 0 mm. If the lesion is believed to be present and is faintly seen but too small to measure, a default value of 5 mm should be assigned. For lesions which fragment/split add together the longest diameters of the fragmented portions; for lesions which coalesce, measure the maximal longest diameter for the “merged lesion.”

Clinical Lesions. Clinical lesions will only be considered measurable when they are superficial and  $\geq 10$  mm as assessed using calipers (eg, skin nodules). For the case of skin lesions, documentation by color photography including a ruler to estimate the size of the lesion is recommended. If feasible, imaging is preferred.

Chest X-Ray. Chest CT is preferred over chest X-ray, particularly when progression is an important endpoint, since CT is more sensitive than X-ray, particularly in identifying new lesions. However, lesions  $\geq 20$  mm on chest X-ray may be considered measurable if they are clearly defined and surrounded by aerated lung.

CT, MRI. CT is the best currently available and reproducible method to measure lesions selected for response assessment. This guideline has defined measurability of lesions on CT scan based on the assumption that CT slice thickness is 5 mm or less. When CT scans have slice thickness greater than 5 mm, the minimum size for a measurable lesion should be twice the slice thickness. MRI is also acceptable in certain situations (eg, for body scans). Other specialized imaging or other techniques may also be appropriate for individual case (1). For example, while PET scans are not considered adequate to measure lesions, PET-CT scans may be used providing that the measures are obtained from the CT scan and the CT scan is of identical diagnostic quality to a diagnostic CT (with IV and oral contrast).

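### Appendix 9 contradicts itself on whether a palpable lymph node with a short axis of 10 to <15 mm is measurable

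*Protocol*

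**What the plan says.** Inclusion criterion I 03 (Section 5.1) asks for "At least 1 measurable lesion (not biopsied at baseline) per RECIST 1.1 criteria". What counts as measurable is defined in Appendix 9 (10.9), with parallel text in 10.10.2.

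- **Appendix 9, Methods for Evaluation of Measurable Disease:** "Clinical lesions will only be considered measurable when they are superficial (eg, skin nodules and palpable lymph nodes") and at least 10 mm "diameter as assessed using calipers (eg, skin nodules"). No axis is given, and nodes are not among the examples attached to the size.
- **Appendix 9, Selection of Lesions:** "To be considered pathologically enlarged and measurable, a lymph node must be" at least 15 mm in short axis, a condition worded for CT assessment. Nodes of 10 to <15 mm ("short axis), are considered non-measurable disease") are excluded, with no modality named. For nodes, "At baseline and in follow-up, only the short axis will be measured and followed".
- **Section 10.10.2:** "Clinical lesions will only be considered measurable when they are superficial and" at least 10 mm by calipers, with skin nodules as the only example.
- **Appendix 9, Evaluation of Target Lesions:** for complete response (CR), "Any pathological lymph nodes (whether target or non-target) must have reduction in short axis to <10 mm". Partial response (PR) needs a 30% fall in the sum of target diameters from baseline.

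The primary endpoint is the objective response rate (ORR) by Investigator, confirmed at least 4 weeks later. Central reading is optional and retrospective (Sections 4.2 and 9.4.1).

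**The concern.** A palpable neck node with a short axis of 12 mm is measurable under one paragraph of Appendix 9 and non-measurable under another. Because the 15 mm condition is worded for CT, a site can take the caliper paragraph as the rule for nodes assessed by hand. Eligible primaries are oropharynx, oral cavity, hypopharynx and larynx, so superficial neck nodes are a foreseeable target lesion.

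Two things follow if the caliper paragraph is applied. A participant can meet I 03 on a node that the node-specific rule would make non-target. And the response scale for that node is compressed: the size at which it becomes measurable (10 mm) meets the size below which it counts as CR (<10 mm). That removes the margin which the 15 mm rule provides. The result feeds ORR and the endpoints built on the same response calls: time to response, duration of response and clinical benefit rate. A stored image cannot re-check a caliper reading, so a later central review would not fully repair it.

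**Working it through.** **1. The plan's own figures.** Table 5 gives 8/40 = 20.0% with a 90% Clopper-Pearson interval of 10.4% to 33.2%, and 9/40 = 22.5% with 12.3% to 36.0%. Both reproduce, as do the other nine rows. One misclassified responder in a cohort of 40 therefore moves ORR by 1/40 = 2.5 points.

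**2. Shrinkage needed for nodal CR, from the plan's thresholds alone.** For a baseline short axis b, reaching 10 mm needs a fall of (b − 10)/b. CR needs slightly more, because the reading must be below 10 mm.

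| Baseline short axis (mm) | Fall to 10 mm | 30% PR would be reached at |
|---|---|---|
| 10 | 0.0% | 7.0 mm |
| 11 | 9.1% | 7.7 mm |
| 12 | 16.7% | 8.4 mm |
| 13 | 23.1% | 9.1 mm |
| 14 | 28.6% | 9.8 mm |
| 15 | 33.3% | 10.5 mm |

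The two cuts cross at b = 10/0.7 = 14.3 mm. Below that, nodal CR is easier to reach than PR; from 15 mm upward it is harder. This step needs no assumption about error.

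**3. Measurement error with no true change.** The protocol gives no measurement SD, so the SD (s) is an assumption. Errors are taken as independent and normal. For a node of true short axis t, the chance that a first and a confirming reading both fall below 10 mm is Φ((10 − t)/s)².

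- t = 10 mm: 0.5² = 25% at any s.
- t = 11 mm: 2.5% at s = 1 mm, 9.5% at s = 2 mm.
- t = 12 mm: 0.05% at s = 1 mm, 2.5% at s = 2 mm.
- t = 15 mm: about 0 at s = 1 or 2 mm, and about 0.2% even at s = 3 mm.

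**4. The same over a scan schedule.** The Cohort A1 primary cut-off is about 9 months after the last participant's first infusion, roughly 9 × 52/12 = 39 weeks. Nine-weekly imaging gives scans at weeks 9, 18, 27 and 36, so four follow-up readings is a reasonable setting. In simulation, the true size stays constant, the baseline reading must be at least 10 mm, and a false confirmed nodal CR is two consecutive readings below 10 mm.

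| True short axis (uniform) | SD 1 mm | SD 1.5 mm | SD 2 mm |
|---|---|---|---|
| 10-15 mm | 3.8% | 6.0% | 8.3% |
| 10-12 mm | 10.7% | 17.2% | 22.7% |

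Under the 15 mm short-axis entry rule, the corresponding figure is below 0.02% at these SDs, even for a node of exactly 15 mm.

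**5. What these percentages describe.** They apply to one node, taken as the sole or dominant target and measured by calipers. They are not an expected bias in cohort ORR. That would need the share of participants with such a target, which the protocol does not give.

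**The case against.** The strongest defence is that the paragraphs can be read together. The caliper sentence states necessary conditions for a clinical lesion; it does not say that every superficial lesion of 10 mm is measurable. Palpable nodes illustrate what superficial means, and the example next to the size is skin nodules alone. The node-specific rule then governs, and its exclusion of 10 to <15 mm nodes names no modality. This is a fair reading and probably the intended one. It is not the only one, because the 15 mm condition is tied to CT and 10.10.2 leaves nodes out of the same sentence.

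The caliper route is also narrow. Appendix 9 prefers imaging unless a lesion cannot be imaged, the Schedule of Activities (footnote h) requires CT of the neck at baseline and on treatment, and the same method must be used throughout. This stands, and it limits how often the problem can arise. A responder must also have lost any other target lesions, with no progression or new lesion. That stands too, although persisting non-target disease would still leave a PR, which counts in ORR.

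A reader might go further and infer that an unchanged node is scored as a response by rule: admitted on its long diameter, then followed on a short axis already below 10 mm. The documents do not support this. Appendix 9 requires the short axis for nodes at baseline as well as at follow-up, adds only the short axis into the sum, treats nodes below 10 mm as non-pathological, and asks for a reduction to below 10 mm. A node at or above 10 mm on its short axis that stays the same can reach CR only through repeated measurement error.

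**Conclusion.** The inconsistency is real and sits in the operative response criteria. For a palpable node of 10 to <15 mm short axis, Appendix 9 gives two answers on measurability, and 10.10.2 differs in wording from the paragraph it repeats. It bears on I 03 and on the Investigator-assessed primary endpoint. If the caliper paragraph is applied, nodal CR needs less shrinkage than PR for baselines from 10 to about 14.3 mm.

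The false confirmed nodal CR rates of about 4-8% and 11-23% rest on assumed SDs of 1 to 2 mm, independent errors, an assumed spread of true sizes, a caliper-measured sole or dominant target, and a site applying the caliper paragraph to nodes. Few participants are likely to meet all of these. Severity is minor and confidence moderate: this is wording to reconcile, not evidence that the plan sets a 10 mm rule for nodes or that cohort ORR will be materially biased.

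**What to change.** In Appendix 9, Methods for Evaluation of Measurable Disease, remove palpable lymph nodes from the examples in the clinical-lesions item, so that it matches 10.10.2. In Selection of Lesions, add that the 15 mm short-axis threshold for a measurable node applies whatever the method of assessment, including to palpable nodes. It already follows from the appendix that nodes of 10 to <15 mm are then non-target disease.

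The cost is a small wording change. A few candidates whose only candidate target is a small palpable node would not qualify under I 03. If participants are already enrolled, a check of baseline target nodes recorded below 15 mm would show whether any response call depends on the point.

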## Response Criteria

### Evaluation of Target Lesions

- **Complete Response (CR):** Disappearance of all target lesions. Any pathological lymph nodes (whether target or non-target) must have reduction in short axis to <10 mm (<1 cm).

- **Partial Response (PR):** At least a 30% decrease in the sum of the diameters of target lesions, taking as reference the baseline sum diameters.
- **Progressive Disease (PD):** At least a 20% increase in the sum of the diameters of target lesions, taking as reference the smallest sum on study (this includes the baseline sum if that is the smallest on study). In addition to the relative increase of 20%, the sum must also demonstrate an absolute increase of at least 5 mm (0.5 cm). (Note: the appearance of one or more new lesions is also considered progressions).
- **Stable Disease (SD):** Neither sufficient shrinkage to qualify for PR nor sufficient increase to qualify for PD, taking as reference the smallest sum diameters while on study.

### Evaluation of Non-Target Lesions

- **Complete Response (CR):** Disappearance of all non-target lesions and normalization of tumor marker level. All lymph nodes must be non-pathological in size (<10 mm [ $<1$  cm] short axis). Note: If tumor markers are initially above the upper normal limit, they must normalize for a patient to be considered in complete clinical response.
- **Non-CR/Non-PD:** Persistence of one or more non-target lesion(s) and/or maintenance of tumor marker level above the normal limits.
- **Progressive Disease (PD):** Appearance of one or more new lesions and/or unequivocal progression of existing non-target lesions. Unequivocal progression should not normally trump target lesion status. It must be representative of overall disease status change, not a single lesion increase.

Although a clear progression of “non-target” lesions only is exceptional, the opinion of the treating physician should prevail in such circumstances, and the progression status should be confirmed at a later time by the review panel (or Principal Investigator).

